9.5.3 Analyses of Exploratory Efficacy Endpoint(s)

9.6 Safety Analyses

9.6.1 Analyses of Primary Safety Endpoint(s)

The proportion of subjects completing 12 cycles of Kd treatment will be calculated and the associated 95% Cl will be estimated using the Clopper-Pearson method. Per protocol, dose intensity is defined as total actual dose divided by planned dose through cycle 12 or up to disease progression. In this SAP, duration of exposure/protocol specified treatment weeks will be taken into consideration when summarizing dose intensity data. Specifically, relative dose intensity as defined in section 5, number of cycles received, duration of treatment, number of administrations and actual cumulative dose will be summarized descriptively for Cycle 1-12 and tabulated separately, with the same four groups as described in section 9.5.2.

Number and proportion of subjects who had dose modifications (dose reductions, missed dose, etc), and reasons of dose modifications will be summarized for Cycle 1-12, tabulated by the same four groups as described in section 9.5.2. In addition, summary statistics of the difference between protocol specified dose and actual dose received will be provided and tabulated by reasons.

Treatment-emergent adverse events and serious adverse events will be summarized descriptively following methods specified in section 9.6.3. The profile plot for each subject, which includes both actual dose received and treatment-emergent adverse events and serious adverse events during the study will be provided. All analyses of primary safety endpoints will be based on the safety analysis set.

9.6.2 Analyses of Secondary Safety Endpoint(s)

Relative dose intensity, number of cycles received, duration of treatment, number of administrations and actual cumulative dose in Cycle 1-6 and Cycle 7-12 will be summarized respectively, with the same four groups as described in section 9.5.2. Number and proportion of subjects who had dose modifications, and reasons of dose modifications will be summarized for Cycle 1-6, and Cycle 7-12 respectively. In addition, treatment discontinuation along with reasons will be summarized descriptively for Cycle 1-6 and Cycle 7-12. Summary statistics of the difference between protocol specified dose and actual dose received will be provided and tabulated by reasons for

Date: 08 June 2018 Page 19 of 27

Cycle 1-6 and Cycle 7-12 respectively. All analyses of secondary safety endpoints will be based on the safety analysis set.

9.6.3 Adverse Events and Disease-related Events

The Medical Dictionary for Regulatory Activities (MedDRA) version 21.0 or later will be used to code all events categorized as adverse events to a system organ class and a preferred term.

Treatment-emergent adverse events are events starting on or after first dose of investigational product and up to 30 days, inclusive, after the last dose of study treatment.

The subject incidence of adverse events will be summarized for all treatment-emergent adverse events, serious adverse events, and adverse events leading to dose modifications, withdrawal of investigational product, fatal adverse events, and adverse events of interest when defined.

Subject incidence of all treatment-emergent adverse events, serious adverse events, adverse events leading to dose modifications, withdrawal of investigational product, and fatal adverse events will be tabulated by system organ class and preferred term in alphabetical order.

Subject incidence of events of interest (standardized MedDRA queries and/or Amgen customized queries) will also be summarized according to their categories and preferred term.

In addition, summaries of treatment-emergent and serious adverse events occurring in at least 5% of the subjects by preferred term in any treatment arm will be provided in descending order of frequency.

Summaries of treatment-emergent and serious adverse events will be tabulated by system organ class, preferred term, and grade.

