# 7.1.2.2 Lenalidomide

## 7.1.2.2.1 Prescribing Requirements

Lenalidomide, a non-Amgen non-investigational product, will also be used in this study for the KRd treatment arm. Lenalidomide should be administered in accordance with the REVLIMID REMS® program of Celgene Corporation (http://www.revlimidrems.com/.) All physicians who prescribe lenalidomide for research subjects assigned to the KRd arm of this study, and all research subjects enrolled on this study who are assigned to the KRd arm, must be registered in and comply with all requirements of the REVLIMID REMS® program.

Females of childbearing potential (FCBP) must agree to monitoring for pregnancy. In addition, males and FCBP are subject to certain restrictions as detailed in Section 12.5 while receiving lenalidomide.

Protocol Number: 20170596

**Date:** 20 May 2019 Page 53 of 132

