# 7.4.1.2.2 Guidelines for Dexamethasone-related Toxicity

Dexamethasone will be permanently discontinued after 2 dose reductions in the event of additional dexamethasone-related toxicities. At the investigator's discretion, dexamethasone may be tapered prior to complete discontinuation according to institutional practice. The subject may continue on treatment with the other protocol-specified drug(s).

Guidelines for dexamethasone-related toxicities are summarized in Table 7-6.

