#### 10.3.2.3.2 Adverse Events

Subject incidence of all treatment-emergent adverse events will be tabulated by system organ class and preferred term. Tables of fatal adverse events, serious adverse events, adverse events leading to withdrawal from investigational product or other protocol required therapies, and significant treatment emergent adverse events will also be provided.

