9.6.8 Exposure to Investigational Product

Descriptive statistics will be produced to describe the exposure to carfilzomib as described in section 9.6.1 and 9.6.2.

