9.6.9 Exposure to Other Protocol-Specified Treatment

Descriptive statistics will be produced to describe the exposure to non-Amgen non-investigational products (dexamethasone). The number of cycles received, duration of treatment, number of administrations, cumulative dose, number and proportion of subjects with dose modifications, reasons for modification will be summarized descriptively.

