9.6.11 Other Analyses

Cardiovascular events may be summarized by risk group defined by ABC score (Bulter 2008). The information of cardiovascular reasons for screen failure will be captured for exclusion criteria from the IXRS system. If warranted by the completeness of information, the proportion of failure reasons may be summarized.

The use of the dyspnea guidance instructions may be summarized by correlating the dates of reporting of dyspnea adverse events with dates of collection of brain natriuretic peptide (BNP) or N terminal of the prohormone brain natriuretic peptide BNP (NT-ProBNP), serum creatinine, echocardiograms, and evaluations for infection or pulmonary disorders as detailed in protocol Section 12.9. The proportion of subjects in whom dyspnea is reported as an adverse event and undergo each evaluation and the results of these evaluations may be summarized descriptively.

10. Changes from Protocol-specified Analyses

There are no changes to the protocol-specified analyses.

Date: 08 June 2018 Page 22 of 27

11. Literature Citations / References

BladÉ, J., et al. (1998). Criteria for Evaluating Disease Response and Progression in Patients with Multiple Myeloma Treated by High-dose Therapy and Haemopoietic Stem Cell Transplantation. British Journal of Haematology 102(5): 1115-1123.

Durie BG, Harousseau JL, Miguel JS, et al. International Myeloma Working Group.

International Uniform Response Criteria for Multiple Myeloma. Leukemia. 2006; 20(9):1467–73. Erratum in: Leukemia 2006; 20(12):2220. Leukemia 2007; 21(5):1134.

Kaplan, E. L.; Meier, P. (1958). Nonparametric Estimation from Incomplete Observations. J. Amer. Statist. Assn. 53 (282): 457–481. JSTOR 2281868

Kyle, R. A. and S. V. Rajkumar (2009). Criteria for Diagnosis, Staging, Risk Stratification and Response Assessment of Multiple Myeloma." Leukemia: Official Journal of the Leukemia Society of America, Leukemia Research Fund, U.K **23**(1): 3-9.

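### The SAP's table of adverse events leading to withdrawal covers carfilzomib only, while protocol 10.3.2.3.2 also covers the other required drugs

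*SAP*

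**What the plan says.** The adverse event section of the protocol (10.3.2.3.2) lists a table of "adverse events leading to withdrawal from investigational product or other protocol required therapies". The matching sentence in SAP 9.6.3 reads "adverse events leading to dose modifications, withdrawal of investigational product, and fatal adverse events will be tabulated", by system organ class and preferred term. The summary sentence just before it in 9.6.3 has the same limit.

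The SAP is consistent about what the investigational product is. Under its heading on exposure to investigational product (9.6.8) it writes: "Descriptive statistics will be produced to describe the exposure to carfilzomib as described in section 9.6.1 and 9.6.2". The next section (9.6.9) deals with "exposure to non-Amgen non-investigational products (dexamethasone" as a separate class. The protocol classes the two immunomodulatory drugs in the same way. Section 7.1.2.2.1 says: "Lenalidomide, a non-Amgen non-investigational product, will also be used in this study for the KRd treatment arm". Section 7.1.2.3.1 says the same of pomalidomide for the KPd arm.

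The protocol allows a partner drug to end by itself. After two dexamethasone reductions, further dexamethasone-related toxicity means permanent discontinuation of that drug, and "The subject may continue on treatment with the other protocol-specified drug(s" (7.4.1.2.2). Sections 7.4.1.4 and 7.4.1.5 allow lenalidomide and pomalidomide to be discontinued for treatment-related toxicity.

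SAP section 10 states: "There are no changes to the protocol-specified analyses".

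**The concern.** Treatment-emergent and serious adverse events are among the primary endpoints. Both documents send that endpoint to these adverse event sections (protocol 10.3.2.3.1, SAP 9.6.1). The protocol's hypotheses concern tolerability of the combinations, not of carfilzomib alone.

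A reader of the clinical study report who wants to know how often toxicity made a subject give up part of the regimen will go to the withdrawal table. If that table counts only withdrawals of carfilzomib, a subject who stops dexamethasone for toxicity and continues carfilzomib contributes nothing to it. Under the current protocol, the triplet arms have two partner drugs that can be stopped in this way.

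A general SAP update that adds arms and dose tables would not necessarily change this sentence, so the narrower scope could pass into the final analysis unnoticed.

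**Working it through.** **1. The two scopes side by side**

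| Item | Protocol | SAP |
|---|---|---|
| Withdrawal table covers | Investigational product or other required therapies (10.3.2.3.2) | Investigational product (9.6.3) |
| Carfilzomib | Investigational (7.1.1) | Investigational (9.6.8) |
| Dexamethasone | Non-investigational (7.1.2) | Non-investigational (9.6.9) |
| Lenalidomide, pomalidomide | Non-investigational (7.1.2) | Not a study treatment (section 5 lists carfilzomib and dexamethasone) |

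**2. Is investigational product just shorthand for the regimen?** No. SAP section 5 defines study treatment as carfilzomib plus dexamethasone. SAP 9.6.3 uses both terms in one definition: the treatment-emergent window opens at the first dose of investigational product and closes 30 days after the last dose of study treatment. The terms are kept apart, so the withdrawal table, read as written, is for carfilzomib.

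**3. Do other SAP outputs fill the gap?**

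- *Overall treatment-emergent and serious event tables (9.6.3).* The event is counted, but nothing shows that it ended a drug.
- *Adverse events leading to dose modifications (9.6.3).* These are tabulated by system organ class and preferred term, and the sentence does not limit them to carfilzomib. SAP 9.6.1 describes modifications as reductions, missed doses and the like. A permanent stop may be captured there, but it is not named and would not be labelled as withdrawal.
- *Dexamethasone exposure (9.6.9).* Modifications and their reasons are summarised, but not the adverse events by preferred term.
- *Treatment discontinuation with reasons (9.2 and 9.6.2).* The reason is given, not the event. Protocol 7.4.1.1 treats a subject as on protocol treatment for as long as carfilzomib is given, so a subject who stops only a partner drug may not count as discontinued.

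None of these gives adverse events leading to partner-drug withdrawal by system organ class and preferred term.

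**4. Size**

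The documents state no figure for this table, so there is none to reproduce. Let *c* be the number of subjects in an arm of *n* who withdraw from carfilzomib for an adverse event, and *p* the number who stop only a partner drug for one.

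- SAP table: *c*/*n*
- Protocol table: (*c* + *p*)/*n*
- Difference: *p*/*n*, whatever *c* is

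With *n* = 25 (protocol 10.1), each such subject is worth 1/25 = 4.0 points. With *n* = 75, the single Kd group in SAP 3.2, each is worth 1/75 = 1.3 points.

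The documents give no value for *p*. Assuming *p* from 1 to 5 in a 25-subject arm, the shortfall is 4 to 20 points. To show this against sampling error, assume also *c* = 3 and use Clopper-Pearson limits, the beta quantiles B(0.025; x, n−x+1) and B(0.975; x+1, n−x):

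| Assumed *p* | Subjects counted | Incidence | Exact 95% CI |
|---|---|---|---|
| 0 (SAP table) | 3/25 | 12% | 2.5% to 31.2% |
| 1 | 4/25 | 16% | 4.5% to 36.1% |
| 2 | 5/25 | 20% | 6.8% to 40.7% |
| 5 | 8/25 | 32% | 14.9% to 53.5% |

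For comparison, protocol 10.1 gives a half-width of 13.5 points at an incidence of 10%. The same formula reproduces it at x = 2.5. Three omitted subjects (12 points) come close to that half-width and four (16 points) exceed it.

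The counts *c* and *p* are illustrations only. The scope difference in step 1 does not depend on them.

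**The case against.** The strongest reply concerns versions. The SAP is dated 08 June 2018 and says that it details the protocol of 06 March 2018. The wider wording is read from the current protocol of 20 May 2019. A reader might infer that SAP section 10 conceals a change from the protocol. The documents do not support that: the adverse event section of the March 2018 protocol is not available, so the SAP may have matched it. The same dates explain why lenalidomide and pomalidomide are missing. Their arms came with Amendment 3, and the protocol says the SAP will be finalised before database lock. The triplet gap is therefore mainly a matter of an SAP not yet updated. This part of the reply stands.

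A second reply is that partner-drug toxicity is not lost. That also stands. The primary endpoint is treatment-emergent and serious adverse events, and every such event remains in those tables. SAP 9.6.1 adds per-subject plots of dose and events. It would be wrong to conclude that partner-drug intolerance drops out of the primary safety analysis.

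A third reply is that a carfilzomib-only table is coherent, because protocol 7.4.1.1 ties being on treatment to carfilzomib, and the table is labelled accordingly. The label is accurate, but the table is still not the one protocol 10.3.2.3.2 describes. The reply is right that the protocol permits partner-only stops and does not predict them. It says outright only for dexamethasone that the other drugs may go on.

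Finally, a reader might take the 12% discontinuation rate quoted for CHAMPION-1 in protocol 5.4.1 as a carfilzomib rate and add partner-drug stops to it. The protocol does not say which drug those discontinuations refer to, so that sum could count the same subjects twice.

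**Conclusion.** The point holds, with a limited scope. Followed as written, SAP 9.6.3 gives a narrower withdrawal table than protocol 10.3.2.3.2 specifies, and no other planned output gives partner-drug withdrawals by system organ class and preferred term. Within the SAP's own scope the drug left out is dexamethasone. Lenalidomide and pomalidomide join it if the sentence is carried unchanged into the update for the current protocol.

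The supportable size is 4 percentage points for each omitted subject in a 25-subject arm. This assumes that the subject stopped only a partner drug. A subject who later also withdraws from carfilzomib for an adverse event already counts in the overall row, although the partner-drug event is still missing from the preferred-term rows. No total can be given, because the documents contain no partner-drug withdrawal rate.

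The documents do not show an undeclared departure from the protocol the SAP was written for, or a loss of these events from the primary endpoint.

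**What to change.** In SAP 9.6.3, tabulate by arm, by system organ class and preferred term:

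- adverse events leading to withdrawal of carfilzomib;
- adverse events leading to withdrawal of any protocol-required therapy, so that the output matches protocol 10.3.2.3.2;
- the same split by dexamethasone, lenalidomide and pomalidomide, where the recorded action taken allows it.

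State whether permanent discontinuation of a drug counts as a dose modification, so that the two tables do not overlap or leave a gap. If the carfilzomib-only scope is intended, keep it and declare it in SAP section 10 with a reason.

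The cost is a change of SAP wording and a few more tables. One thing should be checked first. Reasons for dose change are recorded for each drug (protocol 7.1.2.1, 7.4.1.1, 7.4.1.2, 7.4.1.4 and 7.4.1.5), but the adverse event record in protocol 12.4 lists relatedness to carfilzomib and an action taken that is not specified by drug. If that field is not drug-specific, the events have to be linked to the dosing records. The by-drug split goes beyond what the protocol requires and can be dropped if the link is not reliable.

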9.6.4 Laboratory Test Results

For hematology, chemistry, and other laboratory values, descriptive statistics for the actual value at each visit and the change from baseline at each post-baseline visit during the study period will be summarized. Subjects with missing data for baseline and/or a scheduled visit will not contribute to the summary table which summarizes the change from baseline to that scheduled visit. Numeric values of each laboratory parameter will

Date: 08 June 2018 Page 20 of 27

be converted to grades according to NCI CTCAE (v4.03) and grade shit from baseline will be summarized.

9.6.5 Vital Signs

The analyses of vital signs, including systolic/diastolic blood pressure, heart rate, respiratory rate and temperature, will be summarized descriptively by scheduled time point for actual value and change from baseline.

9.6.6 Physical Measurements

Any clinically significant abnormal values noted on the physical examination will be reported by the investigator as AEs. No summary of the physical examination data will be provided.

9.6.7 Electrocardiogram

The electrocardiogram (ECG) measurements from this clinical study were performed as per standard of care for routine safety monitoring, rather than for purposes of assessment of potential QT interval corrected (QTc) effect. Because these evaluations may not necessarily be performed under the rigorous conditions expected to lead to meaningful evaluation of QTc data; neither summaries nor statistical analyses will be provided, and these data would not be expected to be useful for meta-analysis with data from other trials.

9.6.8 Exposure to Investigational Product

Descriptive statistics will be produced to describe the exposure to carfilzomib as described in section 9.6.1 and 9.6.2.

9.6.9 Exposure to Other Protocol-Specified Treatment

Descriptive statistics will be produced to describe the exposure to non-Amgen non-investigational products (dexamethasone). The number of cycles received, duration of treatment, number of administrations, cumulative dose, number and proportion of subjects with dose modifications, reasons for modification will be summarized descriptively.

9.6.10 Exposure to Concomitant Medication

The number and proportion of subjects receiving therapies of interest will be summarized by preferred term or category by dosing regimen period and overall as

Date: 08 June 2018 Page 21 of 27

coded by the World Health Organization Drug (WHO DRUG) dictionary. See Appendix Appendix C for a list of selected medications and their groupings.

9.6.11 Other Analyses

Cardiovascular events may be summarized by risk group defined by ABC score (Bulter 2008). The information of cardiovascular reasons for screen failure will be captured for exclusion criteria from the IXRS system. If warranted by the completeness of information, the proportion of failure reasons may be summarized.

The use of the dyspnea guidance instructions may be summarized by correlating the dates of reporting of dyspnea adverse events with dates of collection of brain natriuretic peptide (BNP) or N terminal of the prohormone brain natriuretic peptide BNP (NT-ProBNP), serum creatinine, echocardiograms, and evaluations for infection or pulmonary disorders as detailed in protocol Section 12.9. The proportion of subjects in whom dyspnea is reported as an adverse event and undergo each evaluation and the results of these evaluations may be summarized descriptively.

10. Changes from Protocol-specified Analyses

There are no changes to the protocol-specified analyses.

Date: 08 June 2018 Page 22 of 27

11. Literature Citations / References

BladÉ, J., et al. (1998). Criteria for Evaluating Disease Response and Progression in Patients with Multiple Myeloma Treated by High-dose Therapy and Haemopoietic Stem Cell Transplantation. British Journal of Haematology 102(5): 1115-1123.

Durie BG, Harousseau JL, Miguel JS, et al. International Myeloma Working Group.

International Uniform Response Criteria for Multiple Myeloma. Leukemia. 2006; 20(9):1467–73. Erratum in: Leukemia 2006; 20(12):2220. Leukemia 2007; 21(5):1134.

Kaplan, E. L.; Meier, P. (1958). Nonparametric Estimation from Incomplete Observations. J. Amer. Statist. Assn. 53 (282): 457–481. JSTOR 2281868

Kyle, R. A. and S. V. Rajkumar (2009). Criteria for Diagnosis, Staging, Risk Stratification and Response Assessment of Multiple Myeloma." Leukemia: Official Journal of the Leukemia Society of America, Leukemia Research Fund, U.K **23**(1): 3-9.

• Else if the day is missing and month and year = month and year of enrollment then impute day with 15 unless the day of enrollment is < 15 then impute date of enrollment.

- If the day and month are missing and year = year of enrollment then impute July
 1st
- Else if the day and month are missing and year = year of enrollment then impute July 1st unless the day of enrollment is < July 1st then impute January 1st.

Date: 08 June 2018 Page 26 of 27

Appendix B. Reference Values/Toxicity Grades

Laboratory Values

Safety laboratory values below a distinct limit (eg. detection limit, documented as "< [limit]") will be substituted by half of the limit and values above a distinct limit (documented as "> [limit]") will be substituted by the limit itself for all analyses. A Grade will be assigned to each laboratory based on CTCAE version 4.0 [v4.03: June 14, 2010]. Depending on the toxicity definition, the same result may be assigned to two grading for deviations towards higher or lower values. Values not meeting any of the criteria will be assigned a grade 0.

Date: 08 June 2018 Page 27 of 27

Appendix C. Concomitant Medications

The following therapies of interest will be summarized. The list may be updated upon clinical discretion.

Anti-hypertensives;

Angiotensin-Converting Enzyme (ACE);

Calcium Chanel Blockers;

Cardiac Enzymes;

Diuretics;

Other cardiac medications for pulmonary hypertension: treprostinil, iloprost, bosentan, macitentan, ambrisentan, sildenafil, tadalafil, adempas;

Anticoagulants: aspirin, warfarin, low molectular weight heparin, other platelet inhibitors such as plavix.

Procedures including dialysis, CT's, MRI's, PET scans, VQ scans, pulmonary function tests, lung biopsy, cardiac procedures ECHO, heart catheterization, stress tests.
